Additional information with next generation monoclonal antibodies targeting CGRP receptors (e.g. Airomivig) and other small molecules (e.g. Ubrelvy and Nurtec ODT) have not shown similar liver safety issues. Zavegeptant is a third-generation CGRP receptor antagonist that is structurally unrelated to the first-generation small molecule CGRP receptor antagonists. Liver effects have not been observed with zavegeptant; however, liver safety and blood pressure will be monitored in this study.

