4.3 Schedule of Assessments

Table 1: Schedule of Assessments

Procedure	Screening Visit Day -2 to Day 1	Baseline Visit (Randomization) Day 1	Days 2 through 14 (+/- 1 day)¹	End of Treatment (EOT) Visit or Day 15 (+/- 1 day)²	Post-Treatment Phase Days 16 (+/- 1 day) through Day 29³ (+/- 2 days)	Day 60 (+/- 15 days)	Comments
Informed Consent	X						
Inclusion / Exclusion Eligibility Criteria	X	X					COVID-19 test should be positive by PCR test prior to study entry.

¹ If subjects are planned for release from the hospital prior to Day 15, they should discontinue drug for at least 24 hours and receive the End of Treatment assessments prior to discharge. They will be discontinued from study drug but continue in the study. All early discontinuations should be discussed with the Medical Monitor prior to planned release. Subjects will have follow-up phone calls on Days 15, 22, and 29 to assess 6-point ordinal scale, AEs/SAEs, and concomitant medications & procedures unless they are able to return for in-person visits. Subjects will need to return for at least 1 in-person visit on or before Day 60 to have the complete set of Day 29 assessments completed.

² EOT assessments should be completed after the last dose of study drug is administered and prior to hospital discharge. If the subject remains in the hospital and completes treatment (42 doses), Day 15 assessments are the same as EOT assessments. If the subject has EOT assessments completed prior to Day 15, then the Day 15 visit is a telephone visit.

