Procedure	Screening Visit Day -2 to Day 1	Baseline Visit (Randomization) Day 1	Days 2 through 14 (+/- 1 day)¹	End of Treatment (EOT) Visit or Day 15 (+/- 1 day)²	Post-Treatment Phase Days 16 (+/- 1 day) through Day 29³ (+/- 2 days)	Day 60 (+/- 15 days)	Comments
Clinical Safety Laboratory Testing (Hematology: Hemoglobin, hematocrit, RBC count, WBC count with differentials, and platelets HbA1c Chemistry: Sodium, potassium, chloride, bicarbonate, calcium; glucose, BUN, serum creatinine, total protein, albumin, uric acid, LDH, and CK	X		X	X	X	X	Clinical safety labs collected within 48 hours of signing Informed Consent may be used as the Screening assessments. Clinical safety labs will be collected per protocol on Days 1, 2, 5, 10, 15, 22, and 29. If clinical safety labs are collected as per SOC on any other days and are clinically significant, these values should be entered into the eCRF on Unscheduled Visit Clinical Safety Labs pages. After hospital discharge, clinical safety labs should be done at in-person visits on Days 22, 29, and 60 (if this is an in-person visit). Abnormal laboratory test values related to an SAE should continue to be recorded out to Day 60.

Procedure	Screening Visit Day -2 to Day 1	Baseline Visit (Randomization) Day 1	Days 2 through 14 (+/- 1 day)¹	End of Treatment (EOT) Visit or Day 15 (+/- 1 day)²	Post-Treatment Phase Days 16 (+/- 1 day) through Day 29³ (+/- 2 days)	Day 60 (+/- 15 days)	Comments
eGFR)							
Electrocardiogram (ECG)	X						ECG will be collected per protocol at the Screening Visit. If an ECG is collected as SOC within 48 hours of signing Informed Consent, it may be used as the Screening ECG. If ECGs are collected as per SOC on any other days from Day 1 through Day 29 and are clinically significant, these values should be entered into the eCRF on Unscheduled Visit ECG pages.
Physical Measurements	X				X		Screening, Day 22 (+/- 2 days) and Day 29 (+/- 2 days) only. Physical measurements collected within 48 hours of signing Informed Consent may be used as the Screening assessments. Height collected at screening only.
Sequential Organ Failure			X	X	X		This is completed only if the subject is admitted to the ICU. It should only be

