Chest x-ray	X			X			Chest x-ray required at screening and End of Treatment or Day 15 (if subject is in the hospital on Day 15). If a chest x-ray is collected within 48 hours of signing Informed Consent, this may be used as the Screening chest x-ray assessment. If a chest x-ray is collected as per SOC after Day 15 until Day 29, these data should be entered into the eCRF on Unscheduled Visit Chest x-ray pages.
Serum antibody test for SARS-CoV2 virus				X	X		The serum antibody test should be done no earlier than Day 15 and before Day 60
CCI							

Procedure	Screening Visit Day -2 to Day 1	Baseline Visit (Randomization) Day 1	Days 2 through 14 (+/- 1 day)¹	End of Treatment (EOT) Visit or Day 15 (+/- 1 day)²	Post-Treatment Phase Days 16 (+/- 1 day) through Day 29³ (+/- 2 days)	Day 60 (+/- 15 days)	Comments
							Screening Visit
Liver function tests (LFTs) (AST, ALT, alkaline phosphatase, and bilirubin -Total, Direct, Indirect)	X			X			LFTs will be collected per protocol at the Screening Visit and on Day 15. If LFTs are collected as per SOC within 48 hours of signing Informed Consent, these may be used as the Screening values. If additional LFTs are collected as per SOC on any other days from Day 1 through 29 and are clinically significant, these values should be entered into the eCRF on Unscheduled Visit LFT pages.
Pregnancy Test for women of childbearing potential (WOCBP)	X			X	X Day 29 only	X	Urine test is recommended, but serum may also be done if preferred by Investigator/Staff. WOCBP must have a negative pregnancy test at the Screening Visit before being randomized and treated with IP. If a WOCBP is discharged from the hospital prior to Day 22, a urine pregnancy test should be collected at in-person visits on Days 22 (+/- 2 days), 29 (+/- 2 days), and 60 (+/- 15 days) (if an in-person visit).

Procedure	Screening Visit Day -2 to Day 1	Baseline Visit (Randomization) Day 1	Days 2 through 14 (+/- 1 day)¹	End of Treatment (EOT) Visit or Day 15 (+/- 1 day)²	Post-Treatment Phase Days 16 (+/- 1 day) through Day 29³ (+/- 2 days)	Day 60 (+/- 15 days)	Comments
Sparse PK sampling			X Day 5 (+/- 2 days)				PK sampling should be obtained on Day 5 (+/- 2 days). PK may include samples collected at Pre-dose, 0.5, 1, 2.5 and 5h (all samples collected within +/-0.5h).

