5.3 Exclusion Criteria

1. Subjects in immediate need of invasive mechanical ventilation or extracorporeal membrane oxygenation (ECMO).
2. Subjects with an eGFR of < 30 mL/min, at the Screening Visit
3. Prisoners or subjects who are involuntarily incarcerated
4. Subjects who are participating in any other investigational clinical trial while participating in this clinical trial

5. Subjects who are under the age of 18 years
6. Subjects who are pregnant (all potential female enrollees need to have a negative pregnancy test prior to IP administration)
7. Subjects with multi-organ failure
8. Subjects who have received more than 48 hours of supplemental oxygen prior to randomization
9. Subjects with prior significant pulmonary disease (e.g., severe COPD/ILD/CHF/IPF) are excluded
10. Subjects receiving investigational therapies as part of a formal clinical trial for the treatment of COVID-19. During the course of this study, investigational therapies that may become “standard of care” to treat COVID-19, but are not part of a clinical trial, are allowed.
11. Subjects who are on long-acting CGRP monoclonal antibodies will be excluded including Aimovig® (erenumab), Emgality® (galcanezumab), Ajovy® (fremanezumab), and Vyepti® (eptinezumab). Additionally, the investigational oral CGRP receptor antagonist, atogepant, that is taken daily will also be excluded. Oral CGRP receptor antagonists, Nurtec® ODT (rimegepant) and Ubrelvy™ (ubrogepant) that are typically used PRN infrequently will not be excluded as long the subject was not taking them on a daily basis and does not take them during the current study
12. Subjects who are unlikely to survive for more than 48 hours from the Screening Visit
13. Subjects with any of the following abnormal laboratory values at screening: aspartate AST or ALT greater than 5x ULN or bilirubin greater than 2x ULN
14. Subjects with known active TB, history of incompletely treated TB, suspected or known extrapulmonary TB
15. Subjects with suspected or known systemic bacterial or fungal infections. However, empiric antibiotics are permitted
16. Subjects who have participated in any clinical research study evaluating an IP or therapy within 3 months and less than 5 half-lives of IP prior to the screening visit

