7.2 Dose and Administration

Subjects who are hospitalized will be administered three doses (IN devices) per day of blinded IP (10 mg or matching placebo) to be dosed approximately 8 hours (+/- 2 hours) apart, for up to 14 days (42 doses) of treatment. When possible, if subjects are discharged from the hospital to another acute care medical facility prior to completing treatment, they will be provided with enough of their blinded IP and dosing instructions to continue their Q8h regimen until 42 doses have been completed.

Subjects who are discharged to home prior to completing treatment will be discontinued from study drug. Procedures indicated in Section 4.3.3.2 should be followed.

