8.3.5 Potential Drug Induced Liver Injury (DILI)

Wherever possible, timely confirmation of the initial liver-related laboratory abnormalities should occur prior to the reporting of a potential DILI event. All occurrences of potential DILIs, meeting the defined criteria, must be reported as SAEs as per Section [8.3.2](#).

Potential drug induced liver injury is defined as:

1. ALT or AST elevation > 3 times the upper limit of normal (ULN)

AND

2. Total bilirubin > 2 times ULN, without initial findings of cholestasis (elevated serum alkaline phosphatase)

AND

3. No other immediately apparent possible causes of ALT or AST elevation and hyperbilirubinemia, including but not limited to, viral hepatitis, pre-existing chronic or acute liver disease, or the administration of other drug(s) known to be hepatotoxic.

If any potential DILI is identified and meets the criteria above, the Biohaven Medical Monitor (or designee) should immediately be contacted for further instruction and whether the subject must discontinue from the trial and appropriate follow up requirements.

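### No liver function test is scheduled between the first and last dose, so on-treatment liver monitoring rests largely on routine-care tests that the protocol does not require

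*Protocol*

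**What the plan says.** Section 1.1.2.4.1 recalls that first-generation small-molecule CGRP antagonists affected transaminases. It reports that liver effects have not been seen with zavegepant, and adds that "liver safety and blood pressure will be monitored in this study".

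The liver function test (LFT) row of Table 1 is marked in two columns only, Screening and EOT or Day 15, and its comment reads "LFTs will be collected per protocol at the Screening Visit and on Day 15". On timing, footnote 2 to Table 1 says "EOT assessments should be completed after the last dose of study drug is administered and prior to hospital discharge". Section 7.2 gives study drug "for up to 14 days (42 doses) of treatment".

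Safety laboratory tests have a denser schedule: "Clinical safety labs will be collected per protocol on Days 1, 2, 5, 10, 15, 22, and 29". Their content (Table 1 and Section 6.3.5.1) is haematology, HbA1c, a chemistry list and eGFR. AST, ALT, alkaline phosphatase and the bilirubins are listed separately as LFTs.

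For any other LFT the Table 1 comment begins "If additional LFTs are collected as per SOC on any other days from Day 1 through 29 and are clinically significant", in which case the values go on unscheduled pages. Section 6.3.5 also requires recording of routine-care results that change management.

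Section 8.3.5 defines potential drug-induced liver injury (DILI) by ALT or AST above 3 times ULN with total bilirubin above 2 times ULN, no initial cholestasis and no other apparent cause. When it is identified, the Medical Monitor "should immediately be contacted for further instruction and whether the subject must discontinue from the trial". Section 5.3 excludes subjects only above "AST or ALT greater than 5x ULN or bilirubin greater than 2x ULN". Section 3.2.2, item 1, counts subjects with Grade 3 or 4 laboratory abnormalities at any time on study.

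**The concern.** Three parts of the protocol need liver values while drug is being given: the monitoring commitment, the DILI procedure with its discontinuation question, and the Grade 3-4 laboratory endpoint. The schedule supplies liver values only before the first dose and after the last.

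Two things are at stake. For the individual subject, a rise that begins early in the course need not be seen on a scheduled test until dosing is over. For the between-group comparison, the liver part of the endpoint has one scheduled post-baseline value per subject, supplemented by routine-care values that are kept selectively. Reassurance about the liver drawn from such data would be weakly supported.

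**Working it through.** **1. Length of exposure.** One dose every 8 hours for 14 days gives 14 × 24 / 8 = 42 doses, which reproduces the protocol's figure.

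**2. Scheduled liver tests inside the course.** From Table 1:

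| Column | LFT row | Safety-lab draws |
|---|---|---|
| Screening (Day -2 to 1) | yes | yes |
| Days 2-14 | none | Days 2, 5, 10 |
| EOT or Day 15 | yes, after last dose | yes |
| Days 16-29 | none | Days 22, 29 |
| Day 60 | none | if in person |

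Scheduled LFTs between first and last dose: 0. Safety-lab draws already scheduled in Days 2-14: 3, none of which includes the LFT panel.

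**3. Gap between the two scheduled LFTs.** For a subject tested at Day 15, by difference in day number:
- Nominal: from 15 − 1 = 14 to 15 − (−2) = 17 days.
- With the ±1 day window at Day 15: from 14 − 1 = 13 to 16 − (−2) = 18 days.
- If a routine-care value from 48 hours before consent serves as Screening: up to 18 + 2 = 20 days.

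**4. Comparison with the renal rule.** Section 6.6 requires study drug to stop if eGFR falls below 15 mL/min. eGFR is in the panel drawn on Days 2, 5 and 10, so that rule has scheduled on-treatment data. The liver procedure in Section 8.3.5 has none.

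**5. Interaction with the entry limit.** A subject may enter with AST or ALT up to 5 times ULN. One who enters above 3 times already meets the transaminase part of the DILI definition, so bilirubin is the laboratory value still needed to exceed its threshold. It is not scheduled during dosing.

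**6. Illustrative delay.** Assume that onset is uniform over the 14 dosing days, the abnormality persists to the next test, the full course is given and no routine-care LFT is done. With tests separated by intervals of length L days, mean delay = Σ(L²/2) / 14.
- Day 15 only, L = {14}: 98 / 14 = 7.0 days, or 7.0 × 3 = 21 doses.
- Days 5, 10 and 15, L = {4, 5, 5}: 33 / 14 = 2.36 days, about 7 doses.
- Days 2, 5, 10 and 15, L = {1, 3, 5, 5}: 30 / 14 = 2.14 days, about 6 doses.

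**7. Day 15 wording.** The LFT mark sits under EOT or Day 15, but the comment says Day 15. Footnote 2 and Section 4.3.5 make Day 15 a telephone visit when EOT came earlier. Taken literally, the comment would leave a subject discharged early without an end-of-treatment LFT.

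**The case against.** The strongest reply is that the protocol promises monitoring without stating a frequency, and that it does monitor: LFTs before and after dosing, investigator review of all laboratory reports, SAE reporting of potential DILI, and a DMC that may recommend changes to safety monitoring. The expected risk is also described as low. Section 1.1.2.4.1 attributes the first-generation effects to chemical structure and off-target action, calls zavegepant structurally unrelated, and reports no AST or ALT above 3 times ULN or bilirubin above 2 times ULN in any group of BHV3500-201. This lowers the urgency. It does not close the gap, because that was a single-dose study and this course runs to 42 doses. Section 1.3.1 does cite multiple-dose tolerability up to 14 days.

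A reader might infer that no protocol-required value can reveal liver injury during treatment. The document does not support that:
- SOFA has a hepatic component (Section 6.5.2) and is required on ICU admission, which can fall during dosing, though only for those subjects.
- The list of experimental biomarkers collected on Day 5 is redacted, so nothing can be asserted about its content.
- Section 6.3.5 requires abnormal values judged clinically significant through Day 29 to be repeated. An abnormal end-of-treatment value so judged is followed up, even though Table 1 schedules no later LFT.

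A reader might also infer that the DILI procedure cannot operate during treatment. It can: any LFT may trigger it, including a routine-care one, and subjects are dosed in hospital or in a care facility. What stands is that no routine-care LFT is required, and that Section 6.3.5 generally leaves findings associated with the underlying disease outside clinical significance, so capture is selective.

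Finally, the 7.0-day figure does not describe every subject. Those discharged home early stop drug and have EOT assessments before leaving, so their interval is shorter.

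**Conclusion.** The point holds in a bounded form. There are 0 scheduled LFTs between the first and last of up to 42 doses, although blood is already drawn for safety tests on three days in that period. While drug is being given, the monitoring commitment, the DILI procedure and the Grade 3-4 laboratory endpoint therefore rest on routine-care LFTs that are neither required nor fully recorded, apart from the SOFA hepatic item in ICU subjects and any relevant content of the redacted biomarker list.

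This is a weakness in the assessment schedule, which belongs in the protocol, and not a detail left for the SAP. It is not evidence of a liver risk with zavegepant. The counts come directly from Table 1. The delays (mean 7.0 days against about 2.1 to 2.4) are illustrative and rest on the assumptions in step 6; routine-care testing would shorten the 7.0-day delay wherever it is done.

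**What to change.** Reconcile Section 1.1.2.4.1, the LFT row of Table 1 and Section 8.3.5 so that scheduled liver data exist during treatment. One route is to run the LFT panel on the safety-lab blood already drawn in the treatment phase and to record all results, whether or not judged significant. In the same amendment, change the LFT comment so that it matches its column, EOT or Day 15.

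The cost is a Table 1 amendment, one more panel at the local laboratory on existing draws, and some data entry; no visit or needle is added. No dosing or stopping rule is proposed here. How the DILI criteria should apply to subjects who enter with raised transaminases is for the sponsor to settle when reconciling these sections.

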4.3.1 Screening Phase (Day -2 to Day 1)

Approximately 180 subjects will be screened in this study.

Subjects with PCR-documented COVID-19 infection that necessitates hospitalization with supplemental oxygen will be considered for this study. The screening phase is 48 hours. Before any study procedures are performed, subjects must sign Informed Consent. However, any clinical labs, urinalysis, LFTs, PE, Vitals, SpO₂, FiO₂, NEWS2 assessments, ECG, or chest x-ray collected as per SOC within 48 hours of signing Informed Consent may be used as the Screening assessments.

Concomitant procedures are captured from first dose of study drug through Day 29 except for the start of supplemental oxygen which could start within 48 hours of randomization. This data should be captured on the concomitant procedures page.

After Informed Consent has been signed, subjects will be assessed for eligibility and should be immediately randomized once eligibility is confirmed. Subjects will also undergo all screening procedures prior to randomization, including the collection of Experimental Predictive Biomarkers as detailed in [Table 1](#) and Section 6.3.5.2. If the screening laboratory test results or any eligibility criteria are determined to be unacceptable per protocol, the subject is considered a screen failure and will not be allowed to re-screen for the study.

4.3.2 Baseline Visit / Randomization (Day 1)

The Baseline Visit should occur as quickly as eligibility is confirmed after consent form is signed (and no greater than 48 hours later). An unblinded research pharmacist will be required to dispense medication to the research staff. Screening procedures should be completed as quickly as possible so that the patient is randomized within 48 hours from the start of non-invasive supplemental oxygen. All Baseline Visit procedures are outlined in [Table 1](#).

4.3.3 Treatment Phase (Days 1 – 14 +/-1 day)

Approximately 180 subjects will be screened to randomize approximately 120 subjects. The subjects will be randomized in a 2:1 ratio to the zavegeptant (80 subjects) or placebo (40 subjects) treatment groups. Subjects will receive 10 mg IN zavegeptant or placebo every 8 hours (+/- 2 hours) for approximately 14 days (42 doses). Subjects whose renal function declines to an eGFR of < 15 mL/min will be discontinued from study drug.

4.3.3.1 While Subjects are In the Hospital

During the Treatment Phase, while subjects are inpatient, SpO₂, FiO₂ and ongoing vitals will be collected **each day**. Although these procedures may be collected throughout the day as part of standard of care, for the purpose of data collection for this study, vitals, SpO₂, and FiO₂ will be collected in the eCRF **one time daily**. This data may be collected in the morning (AM) or evening (PM) but should be around the same time every day (within 3 hours) and entered on the eCRF. Arterial Blood Gas (ABG) is not a required assessment per protocol. However, if ABG

is collected as per SOC at any time within 48 hours prior to signing Informed Consent through Day 29, this data should be entered in the eCRF whenever it is collected on Unscheduled Visit ABG pages.

NEWS2 is a collection of ongoing vitals related to: respiration (breaths/min), SpO2 oxygen saturation (%), blood pressure (BP), pulse, consciousness, and temperature to provide a total NEWS2 score. While subjects are inpatient, NEWS2 should be assessed daily. The timing of the NEWS2 for the purpose of the data collection for the study should also correlate with the timing of the collection of the SpO2 and FiO2, and entered in the eCRF.

Subjects will have SAE/AEs monitored as well as concomitant medications and procedures daily.

Clinical safety labs, urinalysis, LFTs, ECGs, and chest x-rays will be collected as specified in [Table 1](#).

If the subject is admitted to the ICU, then SOFA2 will be collected upon admission to the ICU, and will be collected again if subject is still in the ICU at Day 29.

If during the treatment period, subjects are transferred to another care facility, they should continue on study drug with the expectation that the Investigator and Staff will coordinate with the treating facility to obtain, at minimum, safety and primary endpoint data and allow the subject to complete the trial as per protocol.

For the purpose of the 6-point ordinal primary endpoint scale, item number 6 (Not Hospitalized) means discharged from acute care. Transferring a subject to another acute care facility due to COVID-19 challenges does not qualify as a 6 on the ordinal scale. Any operational questions about logistics of a transferred subject should be addressed with the Biohaven Medical Monitor or designee.

If local administration site irritation develops, the PI should call the medical monitor to discuss the dosing plan.

4.3.3.2 *If Subjects are Discharged Prior to Day 15*

If a subject is planned to be discharged from the hospital prior to completing treatment, they will be discontinued from study drug. The Investigator should discuss the discharge plan with the Medical Monitor.

Note: Due to the potential for rebound from withdrawal of an immunomodulating agent, if a subject is withdrawn from drug, they need to be monitored in the hospital for at least 24 hours before release. All End of Treatment (EOT) assessments (see Section 4.3.5) should be collected after the patient's last dose of study drug and prior to discharge. Although subjects will be discontinued from the study drug, they will remain in the study. If possible, subjects should continue with in-person visits as per [Table 1](#). If this is not possible due to COVID-19 restrictions, a phone call should be made to the subject on Days 15, 22, and 29 to collect these assessments: 6-point ordinal scale, AEs/SAEs, and concomitant medications and procedures. If

the subject is unable to return for in-person visits on Days 22 and 29 due to quarantine, subjects will need to return for at least 1 in-person visit on or before Day 60 to have the Day 29 in-person assessments completed.

